## **SUMMARY**

### **1.1. Type of request**

This is a non-pharmacological clinical trial in which we are going to compare two types of hemodynamic management during lung resection surgery.

### **1.3. Title**

Goal Directed Therapy Versus Standard Care in Lung Resection Surgery (GDT-thorax Study).

### **1.4. Protocol Code**

GDT-thorax. NCT03245372

### **1.6. Place of realization**

University Hospital Virgen del Rocío, Seville. General Hospital.

### **1.7. Research Ethics Committee**

Clinical Research Andalusian Central Ethics Review Committee

## **2. GENERAL INFORMATION**

### **A. Trial identificacion**

A.1 Protocol code. GDT-thorax. NCT03245372.

A.2 Title. Goal Directed Therapy Versus Standard Care in Lung Resection Surgery.

### **B. Tipo de Ensayo Clínico**

Non-pharmacological pilot clinical trial with sanitary product.

### **D. Place of realization**

The selection, treatment and follow up of the patients will take place in General University Hospital Virgen del Rocío: Post-anesthesia care unit, Thoracic surgery operating room (number 54) and Thoracic unit.

### 3. RATIONALE

Respiratory insufficiency is the main cause of mortality after thoracic surgery. The administration of high amount of fluids can worsen the respiratory complications. As consequence, fluid regimens in this surgery are restrictive. Nowadays, recommendations of fluid therapy in thoracic surgical procedures are summed up in the article of Chau et al in 2014:

- Total positive fluid balance in the first 24 hours postoperatively should not exceed 20 mL/kg.
- Crystalloid administration should be limited to <2 L intraoperatively and < 3 L in the first 24 hours postoperatively.
- Colloids should only be used to replace an equivalent volume of blood loss if blood is not required (maintain Hb > 80g). Maximum colloid volume = 1 L or an adult
- Urine output > 0.5 mL/kg/h is unnecessary in the early postoperative period unless the patient is at high risk of developing acute kidney injury.
- If increased tissue perfusion is needed postoperatively, appropriate invasive hemodynamic monitoring should be initiated to guide treatment with vasopressors, inotropes or fluid administration (1).

Nevertheless, a restrictive fluid therapy can lead to a situation of hypovolemia, with its corresponding risk of developing acute kidney injury due to low tissue perfusion. To administrate the proper amount of fluids, the concept of goal directed therapy (GDT) has gained widespread, helping us to discriminate what a patient needs in every moment (vasopressors, fluids or both).

There are clear evidences of the superiority of GDT over liberal fluid therapy in high risk patients (2,3), but this evidence is less clear if you compare GDT with normovolemic protocols aiming to get zero fluid balance, specially in patients enrolled in an enhanced recovery after surgery program (ERAS) (4). In cardiac surgery, 2 meta-analysis demonstrated a reduction in postoperative complications, ICU stay and hospitalary stay, but there was not a significant reduction in mortality (5,6).

In lung surgery, there are only two published articles of GDT, Zhang et al (7) in 2013 and Haas et al (8) in 2012. These articles use in their algorithms the systolic volume variation (SVV), a parameter which requires mechanically controlled ventilation (8 mL/kg ideal weight) and sinus rhythm. In this surgery, one lung ventilation, the opening of the thorax and the use of low tidal volume (4-6 mL/kg) makes SVV an unuseful parameter to guide hemodynamic management.

This study is designed to quantify and compare the hemodynamic control of cardiac index in patients who receive either goal-directed therapy or conventional hemodynamic management in lung resection surgery. With the help of the ev1000 clinical platform, we will analyze the percentage of the intraoperative time in which the cardiac index is equal or superior to 2.2 l/min/m^2 (%). At the date of the elaboration of the study, this aspect has never been evaluated before, so we are going to conduct a pilot clinical trial.

## 4. HYPOTHESIS AND OBJECTIVES

### HYPOTHESIS

The investigators hypothesize that the percentage of the intraoperative time in which the cardiac index is equal or superior to 2.2 l/min/m^2 is higher in goal directed therapy.

### PRIMARY OBJECTIVES

The primary aim of this study is to quantify and compare the percentage of the intraoperative time in which the cardiac index is equal or superior to 2.2 l/min/m^2 in patients who receive either goal-directed therapy or standard hemodynamic management in lung resection surgery.

### SECONDARY OBJECTIVES

- To compare lactate, SvcO2 (central venous oxygen saturation) and PaO2/FiO2 ratio (ratio of arterial oxygen partial pressure to fractional inspired oxygen) in the first 24 hours in both groups
- To compare fluid balance (differences between the amount of water taken into the body and the amount excreted or lost) in the first 24 hours in both groups
- To compare the incidence of AKI in both groups
- To compare the incidence of ARDS in both groups
- To compare hospital stay in both groups
- To compare the mortality rate in both groups

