#### Secondary outcome measures:

- Oxygenation and tissue perfusion markers [ Time Frame: Within 24 hours after lung surgery]

- Fluid balance [ Time Frame: After 24 hours of finalization of lung surgery]

1) Inputs:
+ Fluid therapy (intra and postoperative, ml):
+ Insensible fluid input (due to oxidation): 300 ml/24 hours (12.5 ml/h).
+ Oral intake (water, ml):
2) Outputs:
+ Intraoperative bleeding (ml)
+ Urine output 24 hours (ml)
+ Insensible fluid loss: 0.5 ml/kg/h (24h)
+ Intrathoracic drainage (ml)
+ Thoracotomy: 1ml/kg/h surgery (0.5 ml/kg/h in case of video-assisted thoracotomy)

- Observation of acute kidney injury (AKI) [ Time Frame: After 72 hours of finalization of lung surgery]

The AKIN classification/staging system of acute kidney injury		
Stage	Serum creatinine	Urine Output (UO)
1	↑ SCr ≥26.5 μmol/L (≥0.3 mg/dL) or ↑SCr ≥150 a 200% (1.5 a 2×)	UO < 0.5 ml/kg/h during > 6 h
2	↑ SCr >200 a 300% (>2 a 3×)	UO < 0.5 ml/kg/h during > 12 h
3	↑ SCr >300% (>3×) or if baseline SCr ≥353.6 μmol/L (≥4 mg/dL) ↑SCr ≥44.2 μmol/L (≥0.5 mg/dL)	UO < 0.3 ml/kg/h during > 24 h or anuria during 12 h
Stage 3 also includes patients requiring RRT independent of the stage (defined by SCr and/or UO) they are in at the moment they initiate RRT.		

- Observation of acute respiratory distress syndrome (ARDS) [ Time Frame: Within 30 days after lung surgery]

The Berlin Definition of Acute Respiratory Distress Syndrome.
a) Timing: Within 1 week of a known clinical insult or new or worsening respiratory symptoms.
b) Chest imaging: Bilateral opacities, not fully explained by effusions, lobar/lung collapse, or nodules.
c) Origin of edema: Respiratory failure not fully explained by cardiac failure or fluid overload. Need

objective assessment (eg. Echocardiography) to exclude hydrostatic edema if no risk factor present.	
d) Oxigenation:	
Mild	200 mm Hg < PaO 2 /FIO 2 ≤ 300 mm Hg with PEEP or CPAP ≥ 5 cm H 2 O *
Moderate	100 mm Hg < PaO 2 /FIO 2 ≤ 200 mm Hg with PEEP ≥ 5 cm H 2 O
Severa	100 mm Hg ≤ PaO 2 /FIO 2 with PEEP ≥ 5 cm H 2 O
* CPAP may be delivered noninvasively in the mild acute respiratory distress syndrome group.	

- Duration of hospital stay [ Time Frame: Within 30 days after lung surgery]
- Mortality [ Time Frame: Within 30 days after lung surgery ]

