### Anesthetic protocol

1. Basic Anesthetic Monitoring: EKG, BP, SpO2.
2. Placement of peripheral venous line on the opposite arm of the surgery. 16 gauge if possible.
3. Administration of midazolam 2 mg IV if necessary.
4. Thoracic epidural catheter placement: T2-T6.
5. Biespectral index sensor placement.
6. Placement of **TOF-Watch** monitoring.

7. Induction:
  - Fentanyl 2 mcg/Kg IV.
  - Propofol 2 mg/Kg IV.
  - Rocuronium 0,6 mg/Kg, after calibration of TOF-Watch monitor.
8. Orotracheal intubation. Comprobatation of correct placement of double lumen endotracheal tube with flexible bronchoscopy. Bladder catheterization.
9. Mechanical Ventilation, volume control. Tidal volume 8 ml/kg ideal weight, respiratory rate 12-14 breaths per minute. FiO2 40% and positive end-expiratory pressure 5 cm H2O.
10. Sevoflurane for maintenance of general anesthesia, BIS objective between 40 and 60.
11. **Antibiotic prophylaxis** (Cefazolin 2g IV). We repeat cefazolin 2 g three hours after the beginning of the surgery.
12. Placement of an arterial line on the radial artery of the opposite arm of the surgery. Invasive arterial blood pressure monitoring (FloTrac system). Obtaining baseline VSI and CI value. ARTERIAL BLOOD GAS SAMPLING (induction) AND LABORATORY BLOOD TEST (creatinine), ev1000 clinical platform (hemodynamic data collection).
13. **RANDOMIZATION (trial treatment)**, Clinical Trial Unit, HUVR.
14. Central venous catheterization of the internal jugular or subclavian vein of the side of the surgery. VENOUS BLOOD GAS SAMPLING (induction).
15. Placement in lateral decubitus position. Inflation of the bronchial balloon of the double lumen tube after verification with fiberoptic bronchoscopy. Placement of thermal blanket.
16. Alveolar recruitment maneuver in bipulmonary ventilation: With pressure controlled ventilation, we set the inspiratory time at 50%, and we establish the respiratory rate at 12 rpm. The pressure over PEEP (Positive End-Expiratory Pressure) is kept constant at 20 cm H2O. The inspiratory pressure and the PEEP increase simultaneously and progressively from 30/10 to 35/15 and finally to 40/20 cmH2O. This last 40/20 cmH2O recruitment pressure is maintained for 10 cycles. Subsequently, the PEEP decreases gradually, returning to the baseline parameters, maintaining the PEEP at 7 cmH2O. After performing the recruitment maneuver, we return to volume controlled ventilation.

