### **10.2. Statistical methods**

Normality of the data will be assessed using the Kolmogorov-Smirnov test. A descriptive analysis expressing qualitative variables as proportions and quantitative variables as mean (SD) or median and interquartile range (RIC), depending on if they follow a normal distribution or not, will be performed. In order to compare study groups, the Chi squared test or Fisher's exact test for qualitative variables and t Student's test or Mann-Whitney U, when necessary, in quantitative variables will be used. Analysis will be performed using the Statistical Package for Social Sciences (SPSS Inc, Chicago III, U.S.A.) v 19.0.

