### APPENDIX III. Scheduled of visits and assessments

	Preanesthesia visit	Selection (Day -1)	Clinical data (before surgery) (Day -1)	Day of the surgery (Day 0)	First postoperative day (Day +1)	Second postoperative day (Day +2)	Third postoperative day (Day +3)	End of follow-up (día +30)
Clinical evaluation	X							
ASA classification	X							
Inclusion/exclusión criteria		X	X	X				
Informed consent form		X						
Demographic data			X					
Previous diseases/medication			X					
Randomisation				X				
Surgery data				X				
Anesthehesia data				X				
Follow up in post anesthesia care unit				X	X			
Arterial gasometry (lactate, PaO 2 , Hb, pH) *				X	X			
Venous gasometry (SvcO 2 ) *				X	X			
Hemodynamic data (EV1000): CI, SVI, CVP, MAP *				X	X			
Laboraroty test (creatinine, PCR)				X	X	X	X	
Adverse events				X	X	X	X	X
Survival				X	X	X	X	X

\* In anesthetic induction, after 20 minutes of the onset of one lung ventilation, at the end of the surgery, at 4 hours and 24 hours (postoperative).

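### The plan does not say how the repeated lactate, SvcO2 and PaO2/FiO2 samples will be analysed, and its only listed tests ignore the induction value; the SvcO2 induction sample also follows randomisation

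*Combined protocol and SAP*

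**What the plan says.** Section 4 (Secondary objectives) lists a between-arm comparison of lactate, SvcO2 and PaO2/FiO2 "in the first 24 hours in both groups". Section 5.1 gives the outcome as "Oxygenation and tissue perfusion markers [ Time Frame: Within 24 hours after lung surgery". Section 7.2 and the footnote to Appendix III set the sampling times: "In anesthetic induction, after 20 minutes of the onset of one lung ventilation, at the end of the surgery, at 4 hours and 24 hours".

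For comparing arms on quantitative variables, section 10.2 says only that "t Student's test or Mann-Whitney U, when necessary, in quantitative variables will be used". Section 10 names no time point, summary measure, repeated-measures method, baseline adjustment, significance level or multiplicity rule for these markers.

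In the anesthetic protocol of section 5.3, the arterial induction sample is part of step 12. Step 13 is "RANDOMIZATION (trial treatment", and step 14 contains the "VENOUS BLOOD GAS SAMPLING (induction". Surgery starts at step 19, and fluid and hemodynamic therapy by allocated arm is listed at step 21. Section 5.2 places the call for the allocation at the point where the arterial line is in, which agrees with steps 12 and 13. Section 5.5 says the intraoperative anesthesiologist knows the arm.

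**The concern.** Three markers measured five times in 30 patients form a repeated-measures data set, yet the plan offers only tests of one value per patient. Two things follow.

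- **Selection.** The analyst may test any or all of the times and report whichever differs. A reader of the results could not tell a pre-planned comparison from a chance one.
- **Precision.** Each patient has an induction value, and the listed tests make no use of it. With 15 patients per arm, that is information already paid for.

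The order of the venous sample is a separate and smaller matter. Baseline adjustment is cleanest when the baseline precedes allocation. That holds for lactate and PaO2 but not for SvcO2.

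**Working it through.** **Plan's own figure.** The sample size of 30 (15 per arm, section 10.1) comes with no significance level, power, effect size or SD. There is nothing to reproduce, and it is not a wrong figure.

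**Inputs from the documents.** Three markers (section 4), five sampling times (Appendix III), 15 patients per arm (section 10.1), two-sample tests (section 10.2).

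**Assumptions.** Two-sided 0.05 per test, and all correlations; the documents give neither.

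**Step 1: count the comparisons.**
- All five times: 3 × 5 = 15.
- Leaving out the induction lactate and PaO2/FiO2 samples, which precede randomisation: 15 − 2 = 13.
- The four post-induction times: 3 × 4 = 12.
- End of surgery, 4 h and 24 h only, if the section 5.1 time frame excludes the sample during one-lung ventilation: 3 × 3 = 9.

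**Step 2: chance of at least one false positive.** For m independent tests it is 1 − 0.95^m:
- m = 15: 53.7%
- m = 13: 48.7%
- m = 12: 46.0%
- m = 9: 37.0%
- m = 3 (one test per marker): 1 − 0.95^3 = 14.3%

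For correlated data, t tests were simulated at 15 per arm with 20,000 runs, using equal correlation over time within a marker and a lower correlation between markers:

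| Correlation over time / between markers | 3 times | 4 times | 5 times |
|---|---|---|---|
| 0.3 / 0.1 | 36% | 44% | 50% |
| 0.5 / 0.2 | 33% | 40% | 45% |
| 0.7 / 0.3 | 29% | 34% | 38% |
| 0.9 / 0.5 | 21% | 23% | 25% |

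**Step 3: precision given up.** Write r for the correlation between any two times and set the SD at one time to 1.
- Unadjusted difference at one time: SE = √(2/15) = 0.365.
- The same, adjusted for induction: the residual variance is 1 − r². At r = 0.5 that is 0.75, a 25% reduction, and SE = √(2 × 0.75/15) = 0.316. Since 1/0.75 = 1.33, this is worth about a third more patients.
- Mean of the four post-induction values, adjusted: the variance is (1 + 3r)/4 − r². At r = 0.3, 0.5 and 0.7 this is 0.385, 0.375 and 0.285, so SE = 0.227, 0.224 and 0.195.

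An unadjusted t test at one time has 80% power only for a difference of 1.06 SD. For the adjusted mean of four times, the detectable difference is about 0.66, 0.65 and 0.57 SD at those values of r. These last figures assume the same effect at all four times and ignore the one degree of freedom that the covariate costs.

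**Step 4: order of the samples.** The printed order is arterial sample (12), randomisation (13), venous sample (14), start of surgery (19), allocated therapy (21). Induction SvcO2 is therefore a post-randomisation value, drawn when the anesthesiologist may already know the arm. On the printed order it still comes before allocated therapy begins.

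**The case against.** The strongest reply is that these are secondary outcomes of a 30-patient pilot and no confirmatory claim is made for them. Family-wise control is then partly a matter of preference, and an exploratory label would do. That stands, and the fix allows it. It does not answer the loss of the induction value. Nor does section 10.3 cover the gap, since it disclaims power only for major postoperative complications.

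Some stronger readings are tempting, but the documents do not support them.

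- **That each marker will be tested at each of five times.** The text does not say so. A t test on a mean, a change from induction or one chosen time would also fit section 10.2. The defect is that none of these is specified, and five is only the maximum count.
- **That the late SvcO2 draw costs error control or precision.** It does neither. Its risk is bias, and only if the value is used as a baseline covariate or change reference, which the plan does not currently do.
- **That the induction SvcO2 is already affected by treatment.** Arm B is re-evaluated every 10 minutes, but allocated therapy is listed only at step 21. The Arm B figure, which might say when the algorithm starts, is not available in the text read. Any contamination may be small.
- **That SvcO2 and lactate are the only outcomes able to support the primary result.** Section 4 also lists fluid balance, AKI, ARDS, hospital stay and mortality. Lactate is itself a management objective in Arm A, so it is not a neutral check.

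**Conclusion.** The concern holds as a gap in specification with a cheap remedy. The listed two-sample tests leave the repeated samples without a defined analysis and make no use of the induction value. The range for a chance finding, 37% to 54% if independent and 21% to 50% if correlated, rests on the assumed 0.05 level, the assumed correlations and which times count. Under every count and correlation tabulated, it is well above 5%. The 25% reduction in residual variance rests on an assumed correlation of 0.5 between induction and later values, less one degree of freedom.

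The SvcO2 sampling order is a minor, conditional bias issue. It matters because baseline adjustment, the natural remedy, would use that value. Overall this is a worthwhile improvement rather than a threat to the trial.

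**What to change.** **Section 10.2.** Add one paragraph:
- For each marker, fit one model (a mixed model or ANCOVA, on a log or rank scale if the data are skewed) to the post-induction values, adjusted for the induction value.
- State which sampling times count towards the outcome, so that sections 4 and 5.1 and Appendix III agree.
- Name one contrast per marker in advance and give the reason. The intervention ends at extubation (section 5.4), so 24 h is the sample furthest from it; choosing 24 h would need its own justification.
- Show the other times as estimates with confidence intervals.
- Label the three contrasts exploratory, or adjust across them. Three unadjusted contrasts still carry 14.3% if independent; Holm or Bonferroni holds this to at most 5%.

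**Sections 5.2 and 5.3.** Either draw the venous induction sample before the allocation call, or state that induction SvcO2 is not a pre-randomisation covariate. The first option means amending both sections together, because section 5.2 ties the call to placement of the arterial line. Reordering steps 13 and 14 alone would make the two sections conflict.

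**Cost.** Slightly more analysis work and, if the sample is moved, an allocation call a few minutes later. No extra patients or samples are needed.

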## 5. CLINICAL TRIAL DESIGN

### 5.1. Outcome measures

#### Primary outcome measures:

- Percentage of the intraoperative time in which the cardiac index is equal or superior to 2.2 l/min/m^2 (%) [Time Frame: During the total duration of the surgery].

#### Secondary outcome measures:

- Oxygenation and tissue perfusion markers [ Time Frame: Within 24 hours after lung surgery]

- Fluid balance [ Time Frame: After 24 hours of finalization of lung surgery]

1) Inputs:
+ Fluid therapy (intra and postoperative, ml):
+ Insensible fluid input (due to oxidation): 300 ml/24 hours (12.5 ml/h).
+ Oral intake (water, ml):
2) Outputs:
+ Intraoperative bleeding (ml)
+ Urine output 24 hours (ml)
+ Insensible fluid loss: 0.5 ml/kg/h (24h)
+ Intrathoracic drainage (ml)
+ Thoracotomy: 1ml/kg/h surgery (0.5 ml/kg/h in case of video-assisted thoracotomy)

- Observation of acute kidney injury (AKI) [ Time Frame: After 72 hours of finalization of lung surgery]

The AKIN classification/staging system of acute kidney injury		
Stage	Serum creatinine	Urine Output (UO)
1	↑ SCr ≥26.5 μmol/L (≥0.3 mg/dL) or ↑SCr ≥150 a 200% (1.5 a 2×)	UO < 0.5 ml/kg/h during > 6 h
2	↑ SCr >200 a 300% (>2 a 3×)	UO < 0.5 ml/kg/h during > 12 h
3	↑ SCr >300% (>3×) or if baseline SCr ≥353.6 μmol/L (≥4 mg/dL) ↑SCr ≥44.2 μmol/L (≥0.5 mg/dL)	UO < 0.3 ml/kg/h during > 24 h or anuria during 12 h
Stage 3 also includes patients requiring RRT independent of the stage (defined by SCr and/or UO) they are in at the moment they initiate RRT.		

- Observation of acute respiratory distress syndrome (ARDS) [ Time Frame: Within 30 days after lung surgery]

The Berlin Definition of Acute Respiratory Distress Syndrome.
a) Timing: Within 1 week of a known clinical insult or new or worsening respiratory symptoms.
b) Chest imaging: Bilateral opacities, not fully explained by effusions, lobar/lung collapse, or nodules.
c) Origin of edema: Respiratory failure not fully explained by cardiac failure or fluid overload. Need

objective assessment (eg. Echocardiography) to exclude hydrostatic edema if no risk factor present.	
d) Oxigenation:	
Mild	200 mm Hg < PaO 2 /FIO 2 ≤ 300 mm Hg with PEEP or CPAP ≥ 5 cm H 2 O *
Moderate	100 mm Hg < PaO 2 /FIO 2 ≤ 200 mm Hg with PEEP ≥ 5 cm H 2 O
Severa	100 mm Hg ≤ PaO 2 /FIO 2 with PEEP ≥ 5 cm H 2 O
* CPAP may be delivered noninvasively in the mild acute respiratory distress syndrome group.	

- Duration of hospital stay [ Time Frame: Within 30 days after lung surgery]
- Mortality [ Time Frame: Within 30 days after lung surgery ]

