**Arm B: Goal directed therapy**

[figure not shown]
The hemodynamic algorithm will be based on systolic volume index and fluid challenges. FloTrac sensor (this sensor connects to any existing arterial catheter and provides advanced hemodynamic parameters through pulse contour analysis) and EV1000 clinical platform (clinical platform from Edwards Lifesciences that provides advanced hemodynamic monitoring) will be used to calculate cardiac index and systolic volume index. The goal directed therapy target value is a cardiac index equal or superior to 2.2 l/min/m^2.

3 steps:

\*\* Bolus is administered until IC  $\geq$  2.5 l / min / m^2 or SVI increase is  $<$  10%.

- Step 2: ¿Mean Arterial Pressure (MAP)  $\geq$  65 mm Hg?

- Step 3: Reevaluate steps 1 and 2 every 10 minutes. In all cases, supplementary fluids will be administered to replace blood loss. RBC concentrates will be transfused to maintain hemoglobin above 8 g/dl. If coagulopathy is suspected, it will be corrected according to rotational thromboelastometry.

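### The fluid-balance formula counts fluid given over surgery plus 24 h but urine and insensible loss over 24 h only, and lists no blood-product input

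*Combined protocol and SAP*

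**What the plan says.** Section 5.1 (Secondary outcome measures) sets the outcome and its time frame as "Fluid balance [ Time Frame: After 24 hours of finalization of lung surgery".

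The terms that matter here are:

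- **Inputs:** "Fluid therapy (intra and postoperative, ml" and "Insensible fluid input (due to oxidation): 300 ml/24 hours (12.5 ml/h". Oral water is the only other input.
- **Outputs over 24 h:** "Urine output 24 hours (ml" and "Insensible fluid loss: 0.5 ml/kg/h (24h".
- **Outputs tied to surgery:** "Intraoperative bleeding (ml" and "Thoracotomy: 1ml/kg/h surgery (0.5 ml/kg/h in case of video-assisted thoracotomy". Chest drainage is also subtracted, with no window given.

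The secondary objective in section 4 refers only to the first 24 hours, without an anchor. In section 5.3, the Arm B text states that "RBC concentrates will be transfused to maintain hemoglobin above 8 g/dl" and allows for correction of coagulopathy. The fluid-balance list has no line for blood products. The visit schedule in Appendix III has no separate row for urine or fluid balance.

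**The concern.** A balance is interpretable only if every term covers the same period. Here the fluid input spans surgery plus 24 h, while urine and insensible loss span 24 h. Fluid given during surgery can therefore be added without the urine it produced being subtracted. Blood lost in surgery is subtracted with no listed term for blood given back.

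The Rationale (section 3) names fluid overload as the respiratory hazard in this surgery, and this outcome would show whether goal-directed therapy costs extra fluid. Fluid and vasoactive management is what differs between the arms. Urine and transfusion may follow from that management, so an error in either need not cancel.

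**Working it through.** **The plan's own figure.** The only derived number in the formula is the hourly rate of metabolic water: 300 / 24 = 12.5 ml/h. It reproduces exactly. The problem is the definition of the outcome, not this sum.

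**Do the windows match?** Let surgery last h hours. Fluid input runs for h + 24 hours.

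- If the 24 h starts at the end of surgery, h hours of intraoperative urine are missing.
- If it starts with surgery, intraoperative urine is in, but collection stops 24 - h hours after surgery ends. Fluid is still counted for the last h hours.

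The first is the plain reading, because the list labels its other surgery-related losses as such and does not label urine. Either way the urine window is h hours short. So is the insensible term: at 70 kg and 3 h, 0.5 x 70 x 24 = 840 ml against 0.5 x 70 x 27 = 945 ml.

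**Size per patient, plain reading.** The inputs are 0.5 ml/kg/h insensible loss and 12.5 ml/h metabolic water (both section 5.1). Weight w, duration h and urine rate u are assumptions, since the documents give none of them.

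Net overstatement = u·w·h + 0.5·w·h - 12.5·h

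With w = 70 kg and h = 3 h:

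| Term | u = 0.5 | u = 1 |
|---|---|---|
| Urine not subtracted | 105 | 210 |
| Insensible loss not subtracted | 105 | 105 |
| Metabolic water not added | -37.5 | -37.5 |
| Net (ml) | 172.5 | 277.5 |

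Over 60-80 kg, 2-4 h and 0.5-2 ml/kg/h, the net runs from 95 ml (60 + 60 - 25) to 750 ml (640 + 160 - 50).

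For scale only, the 20 mL/kg recommendation cited in the Rationale is 1400 ml at 70 kg, so 172.5-277.5 ml is 12-20% of it. That figure is background and not a trial criterion.

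**Size between arms.** The insensible terms are imputed from weight and time, so in expectation they affect both randomised arms alike. A chance difference of 1 h in mean duration would contribute 0.5 x 70 - 12.5 = 22.5 ml. What remains comes from urine and blood:

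- **Urine** (gap x 70 kg x 3 h): 0 ml at no gap; 52.5, 105 and 210 ml at gaps of 0.25, 0.5 and 1 ml/kg/h. Omission overstates the balance of the arm that passes more urine during surgery.
- **Blood**, if not counted (assumed 250-300 ml per unit): each extra patient given one unit in an arm of 15 (section 10.1) shifts that arm's mean by 250/15 = 17 ml to 300/15 = 20 ml. Omission understates the balance of the arm transfused more.

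**The case against.** The strongest reply is that this is loose wording and not a rule that leaves anything out. Four parts of it deserve an answer.

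- **Urine.** The start of the 24 h is not stated, and section 4 describes fluid balance as water taken in less water excreted or lost, which would include intraoperative urine. This stands to the extent that exclusion of intraoperative urine is the plain reading and not an explicit instruction. It does not rescue the formula, because no 24-hour urine window fits the input window. The windows would agree if the whole balance ran for 24 h from the start of surgery, but that contradicts the time frame in section 5.1.
- **Losses during surgery.** The formula does subtract bleeding and the hourly Thoracotomy term. This stands. If the Thoracotomy line is meant to replace basal insensible loss during surgery, the 105 ml is not missing and the net falls to 67.5-172.5 ml (105 - 37.5 to 210 - 37.5). Extending the basal term without settling this could count a loss twice.
- **Blood.** Red cells may be intended under fluid therapy, which is not defined. This also stands: blood is not listed, but it is not shown to be excluded.
- **Stakes.** This is one secondary outcome in a 30-patient pilot.

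A reader might go further and infer that the formula biases the comparison of the arms. The documents do not support that. They give no intraoperative urine output or transfusion rate by arm, and the bias is zero if both are equal. Nor does the per-patient overstatement measure such a bias, since part of it is imputed equally in both arms.

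**Conclusion.** The outcome definition is wrong as written, and the matter is minor. The input and output windows cannot be reconciled under the stated time frame, and bleeding is subtracted without a listed input for transfused blood. On the plain reading each patient's balance is overstated by a net 172.5-277.5 ml, which rests on assumed values of 70 kg, 3 h and 0.5-1 ml/kg/h of urine, and on the Thoracotomy line being additional to basal loss.

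The arms' balances can be distorted through urine or blood, by the conditional amounts shown above, starting from zero. That is a plausible risk and not a demonstrated effect. The primary outcome, time with cardiac index at or above 2.2 l/min/m², does not depend on this formula.

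**What to change.** In section 5.1 and on the CRF:

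1. State one window for every input and output, for example from the start of surgery to 24 h after its end.
2. Record urine as the intraoperative volume plus the 24 h postoperative volume.
3. Apply metabolic water and insensible loss over that same window, using the hourly rates already given.
4. State whether the Thoracotomy line is added to basal insensible loss during surgery or replaces it.
5. List transfused blood products (ml) as an input.
6. Give the same window in the section 4 objective.

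The cost is formula and CRF wording. Step 8 of the anesthetic protocol already places a bladder catheter before surgery, so intraoperative urine can be read without a new procedure. The one point needing care is item 4, to avoid counting a loss twice.

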## **8. EFFICACY ASSESSMENT:**

### **8.1. Efficacy assessment:**

This evaluation will be made to all randomized patients:

- Hemodynamic control of the cardiac index.
- Incidence of acute renal failure.
- Incidence of acute respiratory distress syndrome, pneumonia, need for invasive or non-invasive mechanical ventilation.
- Incidence of postoperative nausea and vomiting.
- Incidence of atrial fibrillation.

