### **10.3. Study limitations**

The clinician performing the procedure cannot be blinded to the assignment of the treatment arm. The intervention is limited to the intraoperative period since the patients are extubated in the operating room. The follow up of postoperative morbidity and mortality is limited to one month. The study is not designed to have sufficient power to detect significant differences in major postoperative complications.

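### The severe oxygenation row of the ARDS definition has its inequality reversed, so ratios below 100 meet no category and ratios above 300 pass the oxygenation criterion

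*Combined protocol and SAP*

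**What the plan says.** The protocol lists ARDS among the secondary outcome measures in Section 5.1: "Observation of acute respiratory distress syndrome (ARDS) [ Time Frame: Within 30 days after lung surgery". The case definition follows in a table headed as the Berlin definition, with four items: timing, chest imaging, origin of edema, and oxygenation. The oxygenation item has three rows. The mild row takes ratios above 200 and up to 300, on PEEP or CPAP of at least 5 cm H2O. The moderate row takes ratios above 100 and up to 200, on PEEP of at least 5 cm H2O. The severe row is printed as "100 mm Hg ≤ PaO 2 /FIO 2 with PEEP ≥ 5 cm H 2 O".

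The outcome is used in two other places. Section 4 sets the secondary objective "To compare the incidence of ARDS in both groups", and Section 8.1 includes it in the efficacy assessment: "Incidence of acute respiratory distress syndrome, pneumonia, need for invasive or non-invasive mechanical ventilation". Nothing else in the document restates or corrects the severe threshold.

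**The concern.** The cut-offs fall as the grade rises from mild to moderate, and the moderate row stops just above 100. The severe row should therefore take ratios of 100 and below. The printed row takes 100 and above instead.

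This matters because the table is the only ARDS case definition in the document, and a patient must meet some oxygenation row to count as a case. Applied literally, the rule leaves out the most hypoxemic patients and admits ratios that are not low enough for even the mild grade. Section 3 names respiratory insufficiency as the main cause of death after thoracic surgery and says that large fluid volumes can worsen respiratory complications. ARDS is thus a relevant harm outcome for a trial that compares hemodynamic strategies.

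**Working it through.** The plan states no figure to reproduce here. The check is to apply the three rows to the range of possible ratios, first as printed and then with the severe inequality reversed.

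**Inputs** (Section 5.1, oxygenation item; r is PaO2/FiO2 in mm Hg and PEEP is taken to be at least 5 cm H2O):

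- Mild: 200 < r ≤ 300
- Moderate: 100 < r ≤ 200
- Severe as printed: 100 ≤ r
- Severe with the sign reversed: r ≤ 100

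**Results:**

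| Ratio r | Rows met as printed | Rows met with severe r ≤ 100 | Does meeting the oxygenation criterion change? |
|---|---|---|---|
| below 100 | none | severe | yes: wrongly not met as printed |
| exactly 100 | severe | severe | no |
| above 100 to 200 | moderate and severe | moderate | no |
| above 200 to 300 | mild and severe | mild | no |
| above 300 | severe | none | yes: wrongly met as printed |

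Spot values: r = 80 and r = 99.9 meet no row as printed and the severe row after reversal. r = 150 meets two rows as printed and only the moderate row after reversal. r = 350 meets the severe row as printed and no row after reversal.

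Three things follow.

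1. *Gap.* Every ratio below 100 fails the oxygenation item.
2. *Spurious pass.* Every ratio above 300 on PEEP of at least 5 passes it. This alone does not make a case. Timing and bilateral opacities are still required, and so is the edema criterion: "Respiratory failure not fully explained by cardiac failure or fluid overload".
3. *Double grading.* Ratios above 100 and up to 300 fall in two grades. This does not alter incidence, and no analysis by grade is planned.

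Reversing the one sign removes the gap, the spurious pass and the double grading together: each ratio up to 300 then falls in exactly one row, and none above 300 does. That supports reading the printed row as a slip rather than a deliberate rule.

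**Scale.** Section 10.1 plans 30 patients, 15 per arm. One misclassified patient would move an arm's incidence by 1/15 = 6.7 percentage points. The document gives no expected ARDS incidence, so the number of such patients cannot be calculated.

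**The case against.** The printed error is hard to dispute. The case on the other side is about how much it matters, and much of it stands.

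- *A single ratio is not a patient.* The outcome is ARDS at any time within 30 days. A patient with one ratio below 100 would still count, even on the literal text, if another ratio from 100 to 300 on PEEP of at least 5 was recorded while the other criteria held. Only a patient whose qualifying ratios are all below 100 is lost. This is correct and narrows the effect.
- *Other rules may act first.* Section 6.3 lists a need for ICU transfer as a reason for withdrawal. If patients with ratios below 100 are usually transferred (an assumption; the document does not say so), withdrawal could determine whether the event is recorded. Against this, Sections 8.1 and 10.4 keep all randomized patients in the evaluation. Scheduled blood gases also end at 24 hours (Section 7.2 and Appendix III), so later ratios depend on unscheduled samples.
- *Ratios above 300 matter little in practice.* Such a patient is unlikely to meet the imaging and respiratory-failure criteria. This also stands.
- *The intended rule is recognizable.* The heading and the falling cut-offs show what was meant. That is likely to limit the harm, but a prespecified outcome should not rely on assessors silently overriding its text, since they might do so inconsistently and without a record.
- *Low stakes.* Section 10.3 says of the trial: "The study is not designed to have sufficient power to detect significant differences in major postoperative complications". The primary outcome and the sample size are untouched.
- *It could be a PDF reading error.* The neighboring inequality signs, including the one for PEEP in the same row, are intact, so nothing supports this. A glance at the source file would settle it.

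These points keep the importance modest. None of them makes the row correct.

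**Conclusion.** The severe row is wrong as written. Read literally, a ratio below 100 meets no oxygenation grade and a ratio above 300 on PEEP of at least 5 meets the severe one; classification as meeting or not meeting the criterion is unchanged from 100 to 300. The conclusion rests only on the three printed rows and on the requirement that one of them be met for a case.

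The row should be corrected because it sets a decision threshold for a stated secondary objective. The likely effect on results is small, and it is confined to ARDS incidence.

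**What to change.** In the ARDS table of Section 5.1, change the severe row to PaO2/FiO2 ≤ 100 mm Hg with PEEP ≥ 5 cm H2O. The three rows are then disjoint and cover every ratio up to 300.

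The CRF is not among the documents, so check whether it copies this table and correct it there if it does. If any outcomes have already been assessed, confirm which threshold was applied.

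The cost is one symbol in the protocol and possibly one in the CRF. The change concerns outcome classification only and does not touch patient management, the sample size or the primary analysis.
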